6.3.4.4 Secondary Aims, Hypotheses and Analyses

S1: To compare the rates of SARS-CoV 2 infection status between the randomized treatment arms and the control arms to determine the effect of HCQ dose in the prevention of COVID-19 viremia and disease.

Secondary Hypothesis (S1): There is a hydroxychloroquine dose effect on acquisition of SARS-CoV 2 infection status, compared to placebo.

The endpoint will be SARS-CoV 2 infection status, defined as 1) no SARS-CoV 2 test positive during study follow up; 2) SARS-CoV 2 test positive (i.e., at least one positive RT PCR, or both IgM and IgG positive serology) without clinical symptoms (“asymptomatic SARS-CoV 2 test positive”) 3) SARS-CoV 2 test positive with clinical symptoms (“symptomatic SARS-CoV 2 test positive”).

The analysis will be conducted using FAS. Ordinal logistic regression will be used and analysis will start testing the overall daily and weekly dose effect, followed by pairwise/subgroup comparisons if an overall dose effect is detected at 0.05 level.

S2: To compare the rates of SARS-CoV 2 infection status in the non-randomized comparator arm to the randomized groups to assess the impact of chronic weight-based dosing of HCQ for COVID-19 prevention.

Secondary Hypothesis (S2): There is weekly /daily HCQ dose effect on acquisition of SARS-CoV 2 infection, compared to patients who were already on HCQ.

The endpoint will be the same as described for S1. The analysis will include all randomized *in FAS and non-randomized study participants with at least one post-baseline follow-up.*

We will first test for treatment selection bias using the data collected at the baseline. Inverse probability treatment weighting (IPTW)/propensity score, or matched sub-cohort will be considered to adjust for imbalanced participant characteristics. A similar analysis to that of S1 will be used for testing hypothesis S2.

S3: To compare the rate of SARS-CoV 2 infections as measured by serum IgM/IgG in participants receiving HCQ versus placebo.

Secondary Hypothesis (S3): There is weekly /daily dose effect on status of SARS-CoV 2 infection as measured by serum IgM/IgG, compared to placebo.

The endpoint will be serum IgG/IgM status at each participant’s study conclusion, classified as:

1. Negative (consistently negative for both serologies)
2. Indeterminate (IgM positive, with IgG consistently negative)
3. Positive (IgM and IgG positive, or IgG positive)

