The analysis will be conducted *using FAS*. Ordinal logistic regression will be used to study the status distribution differences among three Arms. Similar to the analysis for S1, the analysis will start testing the overall dose effect, followed by the pairwise comparison between each treated arm and placebo.

S4: To compare the seroprevalence of SARS-CoV 2 IgM/IgG positive samples at study entry and study conclusion in all participants receiving HCQ compared to those receiving placebo.

Secondary Hypothesis (S4): There is weekly /daily dose effect on change in SARS-CoV 2 seroprevalence at study conclusion from the baseline, compared to placebo.

Serum IgM/IgG status at baseline and at study conclusion will be classified into the three categories described for S3. **The endpoint** will be a change in serum IgM/IgG status (from negative at baseline to indeterminate or positive at study conclusion, or indeterminate at baseline to positive at study conclusion).

The analysis approach described for S1 will be used to study the dose effect on change in serum IgM/IgG status *based on all randomized subjects*.

S5: To compare the development of clinical symptoms or COVID-19 diagnosis in participants presenting asymptotically at study entry but identified as seropositive by serology at entry between the randomized treatment arms and comparator arm.

Secondary Hypothesis (S5): There is dose effect on development of clinical symptoms or COVID-19 diagnosis.

The endpoint will be the same as that defined for P1. This analysis will include all randomized study participants who, at baseline, have positive serology (IgM or IgG) but are clinically asymptomatic. The analysis approach described for S1 will be used for this analysis.

S6: To compare the clinical COVID-19 disease need for participants in each treatment arm to require emergency room visit, hospitalization, or ability to stay home without hospitalization.

Hypothesis (S6): There is dose effect on incidence of ED visit/hospitalization, compared to placebo.

The endpoint will be rate of COVID-related ED visits or hospitalizations (by end of the planned 8-week follow-up period, or within 30 days after SARS-CoV 2 test positive if the positive test occurs <30 days before the end of the planned 8-week follow-up period).

FAS will be considered. The analysis approach described for S1 will be used for this analysis.

S7: To determine the safety and tolerability of HCQ dosing for preventive strategy against COVID-19.

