6.4 Sample size/power calculation

Power Calculation for original Primary Aim: (based on original Study Protocol, dated 04/06/2020)

To determine if the use of hydroxychloroquine as preventive therapy decreases the rate of acquisition of SARS-CoV 2 infections in Study Participants as compared to placebo.

The sample size and power calculation for the original aim are based on a SARS-CoV 2 infection rate of 10% in the placebo-treated group, and an average of 6.8% in the randomized weekly- and daily- HCQ groups, with a relative reduction of 32%. Based on an alpha=0.05 two-sided test, with 900 subjects per group that are COVID negative at the baseline, and one interim analysis when 50% of participants (450 per group) have completed the study and primary

endpoint data assessment, we will have more than 80% power (82% to be exact using nQuery) to detect a significant HCQ effect if the observed test statistic is ± 2.9626 or $p\text{-value} < 0.003$ in the interim analysis, or ± 1.9685 or $p\text{-value} < 0.0497$ in the final analysis, using an O'Brien-Fleming alpha spending method to ensure an overall type 1 error of 0.05 and assuming that overall COVID positive rate in the weekly- and daily- dose HCQ groups is 6.8% with $n=1800$ in the HCQ treated group and 900 in the placebo treated group. A reduction of 36% can be detected between either one of the HCQ treatment groups and placebo, using the same assumptions. Assuming 5-10% of patients will have SARS-CoV 2 positive at the baseline, we need 1000 per group, with a total of 3000 participants to complete the trial.

Power Calculation for revised Primary Aim: (based on revised Study Protocol dated 04/16/2020 or after)

To determine if the use of hydroxychloroquine as preventive therapy decreases the rate of acquisition of SARS-CoV 2 infections with clinical COVID-19 disease in Study Participants for each randomized treatment arm as compared to placebo.

The revised sample size and power calculation are based on a 10% rate of clinical COVID-19 disease (with laboratory confirmation) in the placebo-treated group, and an average 6.8% rate in the two randomized HCQ-treated groups (weekly and daily dosing groups), with a relative reduction of 32%. We propose two looks; one look (interim analysis) when 50% of the participants have completed the study and primary endpoint assessment (for P1), and a final look when 100% of participants have completed the study.

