Based on an $\alpha=0.05$ two-sided test, chi-square test/logistic regression with odds ratio estimates, and Haybittle-Peto alpha spending method to ensure an overall type I error, the critical value for the interim analysis will be 0.001 and the critical value for the final analysis will be 0.05. For data illustration, we have also included an O'Brien-Fleming spending function approach for controlling type I error with a critical value of 0.0054 for the interim analysis and 0.0492 for the final analysis.

Power calculations are based on $n=900$ or 935 participants per study arm, using a simulation approach ($n=10,000$ simulations) in three correction methods: #1 comparing the weekly and daily HCQ dose arms to the placebo group separately using the Dunnett's step-up approach; #2 comparing the weekly and daily HCQ dose arms to placebo separately using a conservative Bonferroni approach with critical value of 0.025 for each test at the final look; #3 comparing the combined weekly and daily HCQ dose arms to the placebo using a single test.

With Haybittle-Peto boundary and $\alpha=0.05$ at the final look, the Dunnett's step-up correction uses a closed gatekeeping strategy for testing the daily dose arm vs placebo and the weekly dose arm vs placebo separately: the largest p value tested first will be at 0.05; if that fails, the second test will be at p value 0.026, delivered from the last row of Table 2 of Dunnett and Tamhane (1992), and validated based on simulation using R *DunnettTests* package. Likewise, at the interim look, the largest p value tested first will be at 0.001; if that fails, the second test will be at 0.0005.

Table 1. Power for different scenarios using varying methods. Sample size was determined using the Dunnett's Step up method with the Haybittle-Peto boundary.

Haybittle-Peto approach	$p_0=0.1, p_1=0.073, p_2=0.063$		$p_0=0.1, p_1=p_2=0.068$	
Method	n=900	n=935	n=900	n=935
#1 Dunnett's Step up	0.800	0.811	0.770	0.800
#2 Bonferroni	0.784	0.800	0.745	0.760
#3 Daily+weekly arms vs placebo	0.812	0.83	0.819	0.835

p_0 is the rate for the placebo treated group and p_1 and p_2 are the rates for the two treated groups.

O'Brien-Fleming approach	$p_0=0.1, p_1=0.073, p_2=0.063$		$p_0=0.1, p_1=p_2=0.068$		
Method	n=910	n=935	n=900	n=935	n=970
#1 Dunnett's Step up	0.8	0.814	0.76	0.776	0.801
#2 Bonferroni	0.787	0.8	0.741	0.761	0.784
#3 Daily+weekly arms vs placebo	0.815	0.83	0.815	0.83	0.846

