p_0 is the rate for the placebo treated group and p_1 and p_2 are the rates for the two treated groups.

For the primary Aim / hypothesis, we will use Dunnett's Step up approach to test each dose effect vs. placebo, and a sample size of 935 per arm will insure at least 80% power. The power will be higher for some of the secondary Aims (S1-S4 if use the compressed binary endpoint of infection presence or absence), since a single test will be used to study overall dose effect first, followed by subgroup analysis (Correction Method #3)

Assuming 5-10% of patients will be excluded from FAS, we need 1000 subjects per group, with a total of 3000 participants to complete the trial. The power and sample size calculation remained unchanged.

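### SAP 6.4 credits some secondary aims with higher power from a pooled HCQ-versus-placebo test, but S3 describes a three-arm test and S1/S4 do not say the arms are pooled; a three-arm test has less power

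*SAP*

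**What the plan says.** After settling the primary sample size ("a sample size of 935 per arm will insure at least 80% power"), SAP 6.4 adds that power will be higher for some of the secondary aims. It names S1–S4, on condition that the endpoint is reduced to infection present or absent. The reason given is "since a single test will be used to study overall dose effect first, followed by subgroup analysis (Correction Method #3"). The same section lists that method as "3 comparing the combined weekly and daily HCQ dose arms to the placebo using a single test".

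The first step is described differently in SAP 6.3.4.4:

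- **S1:** "analysis will start testing the overall daily and weekly dose effect, followed by pairwise/subgroup comparisons if an overall dose effect is detected at 0.05 level".
- **S3:** "Ordinal logistic regression will be used to study the status distribution differences among three Arms". It then says that, as in S1, an overall dose test comes first and each treated arm is compared with placebo afterwards.
- **S4:** refers back to the S1 approach and uses all randomized subjects.

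None of these three entries says that the two HCQ arms are combined.

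**The concern.** A pooled comparison of two HCQ arms with placebo and an overall comparison of three arms are different tests with different power. The power statement in 6.4 belongs to the first. S3 reads as the second, and so, on its ordinary meaning, does an overall test followed by pairwise comparisons in S1.

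The first test also acts as a gate. In S1 the arm-by-arm comparisons follow only if it is significant at 0.05. If the gate has less power than 6.4 implies, a real effect on infection or seroconversion will be missed there more often than a reader expects, and a negative S1 or S3 will look more conclusive than it is. Leaving the test undefined also leaves room to choose it after the data are seen, although the SAP describes its analyses as defined before database lock.

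**Working it through.** **Inputs, all from the SAP.**
- Rates: "10% rate of clinical COVID-19 disease (with laboratory confirmation) in the placebo-treated group, and an average 6.8% rate in the two randomized HCQ-treated groups". Table 1 splits the HCQ average in two ways: 6.8%/6.8% and 7.3%/6.3%.
- Sample size: 900 or 935 "participants per study arm, using a simulation approach", allocated 1:1:1.
- Level: 0.05, "two-sided test, chi-square test/logistic regression with odds ratio estimates, and Haybittle-Peto alpha spending method to ensure an overall type I error".
- Step-up limits for the primary: 0.05, then 0.0262 (section 6.3.4.3).

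**Step 1: reproduce the SAP's Method #3 figure.** Pooled test, 935 per arm, 10% v 6.8%:
- mean rate p̄ = (0.10 + 2 × 0.068)/3 = 0.0787
- null SE = √[0.0787 × 0.9213 × (1/935 + 1/1870)] = 0.01078
- alternative SE = √[0.10 × 0.90/935 + 0.068 × 0.932/1870] = 0.01141
- power = Φ[(0.032 − 1.96 × 0.01078)/0.01141] = Φ(0.95) = 0.83

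The SAP prints 0.835, and 0.83 for the unequal split, which has the same average. So the pooled two-group test is what lies behind the claim.

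**Step 2: three-arm test at the same inputs.** Noncentrality λ = n Σ(pᵢ − p̄)² / [p̄(1 − p̄)], referred to chi-square on 2 df (critical value 5.99).
- 6.8%/6.8%: λ = 935 × 0.000683/0.0725 = 8.81, power 0.76
- 7.3%/6.3%: λ = 935 × 0.000733/0.0725 = 9.45, power 0.79

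With equal HCQ rates the pooled test has the same noncentrality, (0.032/0.01078)² = 8.81, but is judged against 3.84. The second degree of freedom costs power and gains nothing in that case.

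**Step 3: simulation** (400,000 trials per row, uncorrected chi-square, final look only). This is slightly less favourable to the three-arm test than the approximation in step 2.

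| n per arm | HCQ rates | Pooled, #3 (SAP) | Step-up, primary (SAP) | Three-arm, 2 df |
|---|---|---|---|---|
| 935 | 6.8%/6.8% | 0.831 (0.835) | 0.780 (0.800) | 0.746 |
| 935 | 7.3%/6.3% | 0.831 (0.83) | 0.815 (0.811) | 0.783 |
| 900 | 6.8%/6.8% | 0.818 (0.819) | 0.764 (0.770) | 0.730 |
| 900 | 7.3%/6.3% | 0.818 (0.812) | 0.798 (0.800) | 0.766 |

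Likelihood-ratio and Wald versions of the three-arm test fall within about 0.006 of the Pearson figures. Adding the 0.001 interim look changes each result by less than 0.002.

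**Step 4: gaps at 935 per arm.**
- Three-arm v pooled: 0.831 − 0.746 = 0.085 for equal rates; 0.831 − 0.783 = 0.048 for unequal rates.
- Three-arm v recomputed primary: 0.780 − 0.746 = 0.034 and 0.815 − 0.783 = 0.032. Against the SAP's printed primary figures the gaps are 0.054 and 0.028.

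**Step 5: where the inputs may differ for a secondary aim.**
- *Higher infection rate.* The SAP gives no rate that includes asymptomatic infections. Assuming the same 32% reduction and 935 per arm, three-arm power is 0.79 at an 11% placebo rate, 0.83 at 12% and 0.91 at 15%.
- *S4, all randomized.* At 1000 per arm, three-arm power is 0.777 (equal rates) or 0.811 (unequal), against 0.855 pooled.
- *Only one dose works.* At 10% v 10%/6.8%, 935 per arm, pooled power is about 0.29 and three-arm power about 0.73.

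**The case against.** The strongest reply is that the SAP does not contradict itself. Section 6.4 calls the first step a test of overall dose effect and labels it Method #3. S1 uses nearly the same words in the same order, and S4 follows S1. On that reading S1 and S4 are pooled and the power sentence is right for them. This stands in part. A reader might infer that S1, S3 and S4 all specify a three-arm test, but only S3 names three arms, and no entry mentions degrees of freedom or a global test. For S1 and S4 the fault is that the wording allows two tests. S3's statement that it is similar to S1 favours the three-arm reading without settling it.

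The second reply is that S1 counts asymptomatic infections as well, so its event rate should be at or above the primary's 10% and its power may well exceed the primary's. This also stands. A reader might infer that the claimed gain turns into a loss for every one of these aims. The documents do not support that: 6.4 claims a gain for only some of them, and at an assumed 12% placebo rate the three-arm test reaches 0.83. But the reason 6.4 gives is the form of the test, not a higher event rate, and that reason fails for a three-arm test.

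Third, this is one explanatory sentence about secondary aims. The sample size, the primary test and the type I error are untouched. That is so, and it limits the weight of the point.

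**Conclusion.** The point holds in limited form. The higher-power statement in 6.4 is supported only for a pooled first test. S3 describes a three-arm test, and S1 and S4 leave the choice open. If the first test is three-arm, its power at 935 per arm is about 0.75 or 0.78 in the two Table 1 scenarios: 5 to 9 points below Method #3 and about 3 points below the primary. The 9-point gap belongs to equal HCQ rates and should not be quoted for the unequal split, where it is about 5.

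These figures assume the binary endpoint that 6.4 makes a condition, the primary's event rates and equal sample size. They do not give the power of the planned ordinal models, which depends on a split between categories that the SAP does not state. S2 involves the non-randomized arm and is not covered here.

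**What to change.** 1. In S1, S3 and S4, state whether the first test compares three arms (2 df) or pools the HCQ arms (1 df). Keep the three-arm test in S3, and in S1 and S4 if that is what is meant.
2. In 6.4, delete the higher-power sentence with its reference to Method #3, or replace it along these lines: on the binary endpoint, with 10% on placebo, an average of 6.8% on HCQ and 935 per arm, the overall three-arm test has power of about 0.75 (equal HCQ rates) to 0.78 (7.3%/6.3%). Power is higher if infection on placebo exceeds 10% (about 0.83 at an assumed 12%, 0.91 at an assumed 15%). For S4, at 1000 per arm, it is about 0.78 to 0.81.
3. Do not repair the mismatch by making the pooled contrast the gate. It gains 5 to 9 points when both doses work, but falls to about 0.29 against 0.73 when only one does, and S1 is meant to examine the effect of dose.

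The cost is SAP wording only: no participants, data collection or change to the primary analysis. The stated power of these aims becomes less favourable.

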6.4.1 Sample size reassessment

The adaptive design will allow the study to reassess the rate of SARS-CoV 2 infection with clinical COVID-19 disease observed in the placebo-treated group at the interim look.

6.5 Interim analysis schedule

One interim analysis will be conducted when 50% of subjects have completed the study and primary endpoint assessment.

6.6 Preparing the data for analyses

The interim analysis database will be locked 1 week after the cutoff date. The data are received continually throughout the trial and checked for consistency. Queries will be issued on an ongoing basis. The project statistician will forward statistical programs and data to the DSMB statistician before the scheduled DSMB meeting. The DSMB statistician will replace the dummy random treatment code with the actual treatment code and execute the programs. The DSMB statistician will summarize the findings in a report addressed to the other members of the DSMB.

6.7 Stopping rule

- For the interim analyses of the primary efficacy analysis, Haybittle-Peto boundary stopping rule will be used. Treatment efficacy will be determined, compared to placebo, if the largest p-value is less than 0.001, or if that fails, the second p-value is less than 0.0005.
- DSMB will consider stopping the trial if there is a safety concern to study participants.

7. Data Safety Monitoring Board

Board Membership: The DSMB will be appointed locally for this investigator-initiated study. Members will include:

DSMB Chair/Director: [name] HFHS Cardiovascular Medicine
[contact] Email: [contact]

[name] HFHS Division Head-Nephrology
[contact] Email: [contact]

[name] HFHS Infectious Disease
[Tel:[name]]([contact]) Email: [contact]

[name], HFHS Department of Internal Medicine Rheumatology
[contact] (cell phone) Email: [contact]

[name] HFHS Department of Public Health Sciences (Biostatistician)
[contact] (cell phone) Email: [contact]

The members of the DSMB must be experts in the field, not be involved in the study, and have no conflicts of interest with the study/research.

Safety oversight will be under the purview of the DSMB. The DSMB will meet to assess safety on each arm of the study, to protect the interests of research patients and ensure that they are not exposed to undue risk. The DSMB will evaluate the progress of the trial with regard to data quality, recruitment, accrual and retention, and risk vs. benefit to participants.

The DSMB chair will be provided with a weekly site AE and SAE report to monitor safety. An interim analysis will be done when a half of patients have completed the 8 weeks assessments for an early treatment efficacy or a possible reassessment of study sample-size if the estimation of placebo rate is inadequate. Depending on response to the study intervention, the DSMB may decide it is necessary to stop/continue the trial if 1) there are safety concerns at any point in the trial or 2) there is evidence of treatment efficacy at the interim analysis; or recommendation for trial modification as it may be suggested, or 3) to continue the trial as designed. The DSMB will only stop the clinical trial for safety reasons.

8. Confidentiality

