and the safety analysis will be based on all randomized patients given there may be lag time to get any future COVID-19 test results back after the time of the study enrollment. The primary outcome of the study will be difference in development of COVID-19 disease between randomized arms. As new assays become available for research use for COVID-19 testing, these will be included in subsequent amendments if needed. The trial is also designed to have one interim look when a half of patients have completed the 8 weeks assessments for an early treatment efficacy, or a possible reassessment of study sample-size if the estimation of placebo rate is inadequate. A DSMB will be assembled to review interim analysis results. The DSMB Chair will also be provided a site SAE report weekly for safety review. Depending on response to the study intervention, the DSMB may decide it is necessary to stop/continue the trial if 1) there are safety concerns at any point in the trial or 2) there is evidence of treatment efficacy at the interim analysis; or recommendation for trial modification as it may be suggested, or 3) to continue the trial as designed. The primary aims of the DSMB are to decide if the study is safe to continue at the interim analysis timepoint and to monitor serious adverse events during the trial.

Participant eligibility will be assessed prior to study entry, and a screening questionnaire will be completed. Eligible asymptomatic participants will have study sample collections (whole blood) obtained at study entry. Clinical symptom data will be obtained at study screening and entry, to assess study eligibility focusing on the presence or absence of symptoms suggestive of COVID-19 infection.

The study's purpose and its potential risks and benefits will be explained to potential study Participants. Enrollment of study Participants will be done only after informed consent is obtained and a copy of the consent document is returned to the potential Participant. Consented Participants will be assigned a unique Subject ID that corresponds to the unique identifier assigned to the participant upon completion and submission of the online screening form.

In the event a Participant decides to withdraw consent before the baseline blood or study specimens can be collected, this Participant will be excluded from the study before they are randomized.

Participants will have 8 scheduled study encounters (see schedule of events, section 7.2).

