error of 0.05, the critical value for the interim analysis will be 0.0054 and the final critical value will be 0.0492. With a sample size of 900 per group and  $\alpha=0.0492$ , the power to detect a 32% reduction in COVID-19 disease rate (10% vs 6.8%) between the placebo group and each HCQ treated group would be 87%. Power calculations are also given for placebo rates of 8% and 15% with a 32% reduction in COVID-19 disease rates for the HCQ treated groups. Assuming 5-10% of patients will have SARS-CoVID-2 viremia positive at the baseline, we need 1000 per group with a total of 3000 patients to complete the trial.

Power calculations using simulations for Dunnett’s step up method

Assuming 900 per group and  $\alpha=0.0492$

COVID-19 disease rate in placebo	COVID-19 disease rate in treatment	Power
8%	5.4%	80%
10%	6.8%	87%
15%	10%	98%

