5.4 DSMB Reports

A weekly report to DSMB will include 1) Cumulative report of enrollment and projection; 2) AE and SAE report.

Reports for a scheduled DSMB meeting will include the cumulative daily and weekly reports; safety report; and the efficacy results at the interim analysis session.

6. Statistical Analysis Plan (SAP)

A formal SAP will be developed before study completion or database lock for an interim analysis. Statistical issues not addressed in the study protocol will be addressed in the formal SAP.

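### Protocol 8.3 and SAP 7 each allow the DSMB to act on interim efficacy and then limit stopping to safety, so what an efficacy crossing leads to is contradictory

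*SAP*

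**What the plan says.** **On stopping.**
- Protocol 8.3 and SAP 7 carry the same paragraph. It lists grounds on which the DSMB may decide to stop or continue. The second ground is that "there is evidence of treatment efficacy at the interim analysis". The paragraph ends: "The DSMB will only stop the clinical trial for safety reasons".
- Protocol 4 repeats the list without the closing sentence, and adds: "The primary aims of the DSMB are to decide if the study is safe to continue at the interim analysis timepoint", together with monitoring serious adverse events.
- SAP 6.7, headed as the stopping rule, says for the interim primary efficacy analysis that a "Haybittle-Peto boundary stopping rule will be used". It continues: "Treatment efficacy will be determined, compared to placebo, if the largest p-value is less than 0.001", or failing that if the second p-value is below 0.0005. Its other bullet says the DSMB will consider stopping for a safety concern.
- SAP 5.4 includes "the efficacy results at the interim analysis session" in the DSMB's reports. Under SAP 6.6 the DSMB statistician runs the programs with the actual treatment codes.

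**On the boundary.**
- Protocol 8.3 uses O'Brien-Fleming spending: "the critical value for the interim analysis will be 0.0054 and the final critical value will be 0.0492".
- SAP 6.4 and 6.7 adopt Haybittle-Peto: 0.001 then 0.0005 at the interim, 0.05 then 0.026 at the final look (0.0262 in SAP 6.3.4.3). SAP 6.4 keeps 0.0054/0.0492 for illustration only.

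**The concern.** An efficacy boundary needs a stated consequence. Here one sentence gives the DSMB a choice to stop on efficacy, and the last sentence of the same paragraph removes it. If the SAP boundary were crossed, the DSMB would have to choose between the two sentences after seeing unblinded efficacy results, which is what a pre-specified rule is meant to prevent. The choice decides whether the remainder of a placebo-controlled trial of 3,000 participants goes on. Because the conflict lies inside each document, it does not depend on which protocol version governs.

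**Working it through.** **1. The passages side by side**

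| Source | May efficacy stop the trial? |
|---|---|
| Protocol 4, list of grounds | Yes, at the DSMB's discretion |
| Protocol 8.3 and SAP 7, second ground | Yes, at the DSMB's discretion |
| Protocol 8.3 and SAP 7, closing sentence | No |
| SAP 6.7, first bullet | Called a stopping rule, but the stated result is that efficacy is determined |
| SAP 6.7, second bullet | Speaks of stopping only for safety |

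Two readings remain: a crossing may stop the trial, or it establishes efficacy while the trial continues. Each leaves at least one sentence without effect.

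**2. The plan's own figure, as a check on the simulation**

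Inputs: 1:1:1 allocation, a shared placebo arm, 10% against 6.8% in both active arms, and 900 per arm in total (SAP 6.4). For each active arm j with n per arm, z = (p0 − pj) / √(2·p̄(1 − p̄)/n), where p̄ is the mean of the two observed proportions; p-values are two-sided. The step-up rule succeeds if the larger p < c1 or the smaller p < c2. With final values 0.05 and 0.0262, the probability that at least one arm succeeds is 0.764. SAP Table 1 gives 0.770, so the set-up is close to the SAP's.

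**3. How often the question would arise**

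Same formula, n = 450 (half of 900), c1 = 0.001, c2 = 0.0005, 2,000,000 simulated trials per scenario:

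| Placebo vs both active arms | At least one arm crosses |
|---|---|
| 8% vs 5.4% | 4.4% |
| 10% vs 6.8% | 6.8% |
| 15% vs 10% | 18.7% |

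With half of 935 per arm, the middle row becomes about 7.3%. At 10% vs 6.8%, a crossing at 450 per arm that is not confirmed at 900 per arm occurs in about 0.03% of all trials (1,000,000 simulated).

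**4. The two boundaries (secondary)**

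Overall two-sided alpha per comparison, if the interim can establish efficacy, is 1 − P(|Z1| < a, |Z2| < b), with corr(Z1, Z2) = √0.5 and a, b the normal quantiles of the two p-value limits:
- 0.0054/0.0492: 0.0513, against the protocol's stated 0.05. A final value of 0.0479 would give exactly 0.05.
- 0.001/0.05: 0.0502. A final value of 0.0498 would give exactly 0.05.

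As an illustration, take 45/450 placebo events and the first step, where both active arms must pass. The limit 0.001 needs 19 or fewer events in each active arm (19: z ≈ 3.37; 20: z ≈ 3.22). The limit 0.0054 needs 22 or fewer (22: z ≈ 2.92; 23: z ≈ 2.77).

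**5. The protocol power table, 900 per arm, two-sided**

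| Scenario | Protocol states | SAP final rule (0.05, 0.0262) | 0.0492 (second step 0.0258 assumed) |
|---|---|---|---|
| 8% vs 5.4% | 80% | 0.674 | 0.673 |
| 10% vs 6.8% | 87% | 0.764 | 0.763 |
| 15% vs 10% | 98% | 0.942 | 0.941 |

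The boundary barely moves power. The protocol's figures are not reproduced two-sided under either boundary.

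**The case against.** The best defence is that the text supports one coherent reading. SAP 6.7 says efficacy is determined on a crossing, its only bullet about stopping concerns safety, and SAP 7 closes with the safety-only sentence. On that reading a crossing establishes efficacy and the trial continues. Part of this stands: a reader might infer that a crossing could have no effect at all, and SAP 6.7 rules that out. The rest does not settle the matter, because the efficacy ground in the same paragraph and the name of the boundary still point to stopping.

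Protocol 4 is weak evidence either way. A reader might take its description of the DSMB's primary aims as confining the board to safety, but primary aims do not exclude others.

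On the boundary, a reader might infer an outright contradiction, or that the SAP is barred from changing the protocol's rule because "Statistical issues not addressed in the study protocol will be addressed in the formal SAP". That sentence does not say the SAP may address only such issues. The SAP's choice of Haybittle-Peto is clear. The supplied protocol also appears older than the one behind the SAP: it covers southeast Michigan and excludes pregnant participants, whereas the SAP covers Michigan and Ohio and mentions a revision to include pregnant women. Version drift may explain the mismatch.

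A reader might also size the point by how often the two boundaries disagree. The protocol gives no second-step level, so its crossing rate at 10% vs 6.8% is 5.2%, 9.0% or 17.1%, depending on whether none, 0.0005 or 0.00275 is assumed. That range rests on assumption and does not measure the main point.

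Finally, under the planned 3-month enrolment, uniform accrual would put the interim at about 13/2 + 8 = 14.5 weeks, after enrolment ends at about week 13, so only follow-up would be at stake. However, SAP 2.2 describes a database opened for new enrolment on 26 July 2020, more than three months after recruitment began on 10 April, so that timeline did not hold.

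**Conclusion.** The main point holds as a matter of text. Each document contradicts itself on whether an interim efficacy crossing may stop the trial or only establishes efficacy while the trial continues. At the design effect the question would arise in about 6.8% of trials under the SAP boundary. That figure assumes 450 per arm, both arms effective, two-sided unstratified tests and the SAP's step-up values.

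A reader might infer a loss of power or of error control. The figures do not support that: unconfirmed crossings are about 0.03% of trials, power is about 0.76 under either boundary, and the alpha difference (0.0513 against 0.0502 per comparison) is minor.

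The boundary mismatch is secondary and conditional on which protocol version is current.

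**What to change.** **Main change, before unblinded interim results are seen.** Reconcile the list of grounds and the safety-only sentence in protocol 8.3 and SAP 7, together with the DSMB text in protocol 4, with SAP 6.7. State the consequence of an efficacy crossing once and in identical words in both documents. Which consequence to adopt is for the sponsor and the DSMB. The cost is a few sentences, with no new data.

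**Secondary, after a version check.** If the current protocol still carries 0.0054/0.0492:
- Replace the pair with the SAP's values (0.001 then 0.0005; 0.05 then 0.0262).
- State that the tests are two-sided and that this rule governs.
- Recompute the three-row power table. Changing its alpha label alone would leave 80%, 87% and 98% standing where about 0.67, 0.76 and 0.94 are obtained.

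The rerun is short. Neither edit changes the sample size by itself. The recomputation should also cover the SAP's 0.800 at 935 per arm, for which a check with 200,000 simulated trials gave 0.780.
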